20. Economic impact data (as available), including the following: length of hospital stay, if applicable; number and types of probes used; and, ablation duration, defined as the time elapsed between first ablation probe puncture and removal of the last probe at the completion of the ablation.
21. Follow-up post-ablation treatment, including the number of successful repeat ablations, if applicable, and if patient has been hospitalized since the procedure. If patient has been re-ablated with NeuWave, record ablation procedure parameters as outlined in section 19.1, subsection 1. Record date of registry completion, when applicable.
22. When applicable, the Screening Visit may occur on the same day as the ablation procedure (Visit 2).
23. Record reason for unscheduled visit, as well as AEs (if applicable), and any updates to the relevant concomitant medications and relevant concomitant procedures.
24. Quality of Life and Pain Questionnaires may be administered up to 72 hours prior to the ablation procedure (Day 0).
25. Post-ablation Pain Score must be administered on the day of ablation (Day 0).
26. For Visit 1 through Visit 3, Eastern Cooperative Oncology Group classification (ECOG) performance status is required. After Visit 3, evaluate ECOG, if applicable per site SOC. ECOG may be assessed over the phone.

NOTE 1: All SOC scans of the abdomen/liver, including CT, MRI, and/or PET, taken at the following timepoints (Screening, Ablation Day, and throughout the 5-year follow-up period) should be submitted to the Sponsor through [REDACTED]. SOC Ultrasound scans of the abdomen/liver should also be submitted to the Sponsor, when on the Ablation Day or at any re-ablation visits. A subset of scans will be reviewed by the Central Review Committee to reduce the variability between investigators in assessing scans and to minimize potential bias.

NOTE 2: Patients rolling into this registry from a previous NeuWave trial will only have data collected in the Registry database starting from the time they consent to participate in the registry. Any data previously collected on roll-over patients will remain in the original database in which it was entered into.

ADMINISTRATIVE REQUIREMENTS

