17.9 Analyses to be Conducted

Categorical variables will be summarized descriptively by frequencies and associated percentages. Continuous variables will be summarized descriptively by number of patients, mean, standard deviation, median, minimum, and maximum. Confidence intervals will also be provided for procedure-related variables.

Disposition of Registry Patients

Patient disposition will be summarized using counts and percentages. The number and percentage of patients completed and discontinued along with the specific reasons for discontinuation will be tabulated.

Demographic and Baseline Characteristics

Summary statistics will be provided for patient demographics and pre-operative ablation characteristics.

Primary and Secondary Endpoint Analyses

Regression analysis methodologies will be utilized to explore the relationship between dichotomous clinical outcomes (technical success, technique efficacy, and secondary efficacy rate) and ablation procedure, patient, and provider parameters. Time to event analyses will be used for target lesion recurrence, regional recurrence rate, recurrence-free survival, progression free survival, and overall survival.

Complete details regarding all analysis methodologies including approaches to handle multiple lesions per patient, variable selection techniques, data reduction techniques given the number of potential independent variables, as well as subgroup analyses of interest will be specified in the SAP.

The number and percentage of patients achieving technical success will be summarized and a 95% confidence interval will be provided. A similar summary will be provided for technique efficacy, as well as for the primary and secondary efficacy rates, as previously defined.

Target lesion recurrence rates at each post-ablation scheduled visit will be estimated using the Kaplan-Meier method and 95% confidence intervals will be provided. A similar summary will be provided for the 5-year overall rate. Similar summaries will also be provided for regional recurrence rate, overall and progression-free survival rates for the entire observation period from the ablation procedure date through 5 years of follow-up.

Scores from the EORTC QOL questionnaires and Numeric Pain Rating Scales will be summarized with methodology consistent to the recommendations of the specific survey. Additional endpoints will be summarized with descriptive statistics.

Plans for Interim Analysis

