18.3 Patient Information and Consent

Regulations concerning the protection of patients require that informed consent be obtained, or waiver approved by the IRB/EC where applicable, before a patient may participate in any clinical registry. For this registry, a patient must be consented or waiver approved by the IRB/EC before completing any registry specific procedures. Screening information that are part of SOC procedures may occur and be collected prior to consent, but the data may not be collected for registry purposes until the informed consent form (ICF) has been signed by the patient or waiver from the IRB/EC is received. A patient who signs the consent, or waiver is received, is considered enrolled.

An IRB/EC approved informed consent or waiver, where applicable, must be sought from each patient and must be appropriately documented in the patient's medical record. It is the Investigator's responsibility to obtain written informed consent from prospective patients or retrospective patients with prospective follow-up prior to registry-specific procedures. The Investigator may delegate this responsibility, if appropriately documented.

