1.2 Study Design

This is a multicenter, observational registry that follows patients for a total of up to 5 years from the date of the first liver ablation procedure with either the NEUWAVE Microwave Ablation System or the NEUWAVE Microwave Ablation System with Ablation Confirmation.

This is an “umbrella registry,” which was included as an optional component in other NEUWAVE studies; hence, data from consenting patients who are or will be enrolled in other NEUWAVE soft tissue liver lesion ablation studies will be included in this registry. All other patients will be enrolled and followed prospectively, enrolled retrospectively with prospective, longitudinal follow up, or enrolled retrospectively with all retrospective follow up.

2 Treatment Assignment

This is a single-arm registry where all enrolled patients will be ablated using the NEUWAVE Microwave Ablation System as part of the site’s SOC treatment or per protocol for those patients who are also enrolled in other NEUWAVE studies.

3 Randomization and Blinding Procedures

As this is a single-arm registry, no randomization will occur, and no blinding procedures are required.

4 Interval Windows

Interval windows are provided in the Schedule of Assessments section of the study protocol. No additional windows are planned for analysis purposes.

5 Levels of Significance

No levels of significance are specified as no specific hypotheses about any of the outcomes of interest are being formulated or tested. Two-sided 95% confidence intervals (CI) will be estimated for specific endpoints for descriptive purposes only.

6 Analysis Sets

All Enrolled Set (AES): Consists of subjects who signed informed consent form or retrospectively enrolled with a waiver for signing informed consent form. The AES will be used for disposition of study subjects.

Full Analysis Set (FAS): FAS Consists of subjects who met inclusion/exclusion criteria and to whom the NeuWave Ablation device was utilized during procedure. Primary and secondary endpoints will be analyzed using FAS.

Safety Analysis Set (SAF): SAF Consists of subjects who met inclusion/exclusion criteria and to whom the NeuWave Ablation device was utilized during procedure. Safety endpoints will be analyzed using SAF.

7 Sample Size Justification

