8.6 Analysis of Secondary Endpoints

The number and percentage of patients and lesions achieving secondary efficacy will be summarized and a two-sided 95% confidence interval will be provided based on Clopper-Pearson’s method. Analysis for secondary efficacy rate includes only repeat ablations for target and non-target lesions.

For patient level analysis – secondary efficacy is achieved for a patient when all re-ablations of target lesions and all re-ablations of non-target lesions are defined as a complete ablation by the performing physician. The denominator for subject level analysis will include subjects who had a re-ablation during visit 3 to visit 14 including unscheduled visits.

For lesion level analysis – secondary efficacy is achieved for a lesion when all repeat ablations of that lesion (target and non-target lesions) are defined as complete ablation by the performing physician. The denominator for lesion level analysis will include lesions that had a repeat ablation during visit 3 to visit 14 including unscheduled visits.

Regional recurrence rates will be estimated at patient level. Time-to-event analysis (survival analysis) using Kaplan-Meier’s method will be utilized to estimate the regional recurrence rate at 3-month, 6-month, up to 60-month follow up. Two-sided 95% CI will be estimated for regional recurrence rate. First occurrence of identification of a new lesion outside the initial treatment site(s) during visit 3 to visit 14 including unscheduled visits at patient level will be considered as the “event” for time-to-event analysis at patient level.

Recurrence-free survival rates will be estimated at patient level. Time-to-event analysis (survival analysis) using Kaplan-Meier’s method will be utilized to estimate the recurrence-free survival rate at 3-month, 6-month, and up to 60-month follow up. Two-sided 95% CI will be estimated for recurrence-free survival rate.

An “event” is defined for recurrence-free survival if any of the following conditions are met:

- a. First occurrence of a target lesion recurrence during visit 4 to visit 14 including unscheduled visits at patient level
- b. Identification of a new non-target lesion during visit 3 to visit 14 including unscheduled visits at patient level

c. Deaths from any cause of a patient during the follow up period

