Overall survival rate will be estimated at 3-month, 6-month, and up to 60-month follow up using Kaplan-Meier's method. Two-sided 95% CI will be estimated for overall survival rate.

Scores from the EORTC QOL questionnaires and Numeric Pain Rating Scales will be summarized with methodology consistent to the recommendations of the specific survey. Economic impact of ablation by capturing procedure-related items will be summarized with descriptive statistics.

Incidence of adverse events (AEs) (SAEs) that are deemed at least unlikely related to the procedure or device and all serious adverse events (SAEs) from the start of the ablation procedure through the end of the study will be summarized by MedDRA system organ class (SOC) and preferred term (PT).

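### Patients who consent after their ablation are certain to be alive until consent, yet the planned Kaplan-Meier analysis counts that time as at risk, which biases overall and recurrence-free survival upward by an unknown amount

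*SAP*

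**What the plan says.** **Enrolment routes.** Besides roll-overs from other NeuWave studies, SAP 1.2 says: "All other patients will be enrolled and followed prospectively, enrolled retrospectively with prospective, longitudinal follow up, or enrolled retrospectively with all retrospective follow up". SAP section 6 puts all of them in one Full Analysis Set, which is used for the primary and secondary endpoints.

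**Consent.** Protocol 18.3 requires the investigator to "obtain written informed consent from prospective patients or retrospective patients with prospective follow-up prior to registry-specific procedures". Protocol 9.3 describes the same group as having visits after signing, and reserves the consent waiver for completely retrospective patients. For roll-overs, Note 2 to the Schedule of Assessments says: "Patients rolling into this registry from a previous NeuWave trial will only have data collected in the Registry database starting from the time they consent". Their earlier data stay in the original database.

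**Time origin.** SAP 8.6 gives none. Protocol 17.9 does: "overall and progression-free survival rates for the entire observation period from the ablation procedure date through 5 years of follow-up". It names overall and progression-free survival. For recurrence-free survival the same origin follows from the endpoint definition (assessed at each visit after ablation) and from the reporting times up to 60 months.

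**Estimator.** Overall survival: "Overall survival rate will be estimated at 3-month, 6-month, and up to 60-month follow up using" Kaplan-Meier. For recurrence-free survival, Kaplan-Meier "will be utilized to estimate the recurrence-free survival rate at 3-month, 6-month, and up to 60-month follow up", and its events include "Deaths from any cause of a patient during the follow up period". SAP 8.5 estimates target lesion recurrence both by Kaplan-Meier and as a cumulative incidence with death as a competing risk.

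**Safeguards.** Neither document mentions delayed entry, left truncation or a landmark. SAP 8.7 plans no sensitivity analysis. The subgroups in SAP 8.8 are disease type and confirmation software, for the primary endpoints only.

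**The concern.** A patient ablated two years before the site approached them can sign a consent form only if they lived those two years. Similar patients who died in the interval do not appear by that route. Ordinary Kaplan-Meier from the ablation date puts the survivor in the risk set from Day 0, so the denominators at early times include people who could not have died then. The early hazard is underestimated, and every later survival estimate inherits the error.

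Recurrence-free survival is affected because death is one of its events. Late-consenting roll-overs bring a second problem: recurrences before consent stay in the parent database, so in the registry these patients look free of recurrence over that interval.

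At stake is whether the reported 1-, 3- and 5-year survival describes all patients ablated with the device or partly those who lived long enough to be asked. Nothing in the planned output would show the difference.

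**Working it through.** The documents give no expected survival, event count, late-consent share or lag, so there is no planned figure to reproduce. The check asks what the planned method would report under stated assumptions.

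**Assumptions.** Exponential survival with true 5-year overall survival of 50%, so λ = ln 2 / 60 = 0.01155 per month and S(12), S(36), S(60) = 87.1%, 66.0%, 50.0%. A share f of analysed patients are late entrants. Their lag is uniform on 0 to L months and independent of survival, and they are included only if alive at consent. Follow-up is complete to 60 months.

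**Formula.** For t ≥ L, survival from ablation among late entrants is S_late(t) = L·S(t) / I(L), where I(L) = (1 − S(L)) / λ. The planned estimate is (1 − f)·S(t) + f·S_late(t).

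| f | L (months) | I(L) | S_late(60) | Planned 5-year estimate |
|---|---|---|---|---|
| 10% | 12 | 11.21 | 12 × 0.5 / 11.21 = 53.5% | 0.9 × 50 + 0.1 × 53.5 = 50.4% |
| 25% | 36 | 29.45 | 36 × 0.5 / 29.45 = 61.1% | 0.75 × 50 + 0.25 × 61.1 = 52.8% |
| 50% | 36 | 29.45 | 61.1% | 55.6% |
| 50% | 60 | 43.28 | 60 × 0.5 / 43.28 = 69.3% | 59.7% |

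Simulation of the same four cases gave about 50.2%, 52.7%, 55.5% and 59.7%, which agrees within 0.2 points. With entry at consent, simulated 5-year survival came back to 49.8–50.1%. Across true 5-year survival of 30% to 70%, the bias at 60 months ran from about +0.2 to +11 points.

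**Precision.** At N = 1,500 and S = 50%, the 95% half-width is 1.96 × √(0.5 × 0.5 / 1500) = 2.5 points.

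**Waiver capture.** Suppose half the cohort is sampled retrospectively with L = 36. The chance of dying before consent is 1 − 29.45/36 = 18.2%. If a fraction c of those deaths is captured by waiver, the planned estimate is 0.5 / [1 − 0.5 × (1 − c) × 0.182]. For c = 0, 25, 50, 75 and 100% this gives 55.0, 53.7, 52.4, 51.2 and 50.0%.

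**Recurrence-free survival.** Add 5-year recurrence of 60%, independent of death, so the recurrence-free probability at 36 months is 0.4^(36/60) = 57.7%. The true value is 57.7% × 66.0% = 38.1%. Take f = 25% and L = 36.
- Consented retrospective patients with chart recurrences captured: S_late(36) = 36 × 0.660 / 29.45 = 80.6%. The estimate is 0.75 × 38.1 + 0.25 × (57.7% × 80.6%) = 40.2%.
- Late-consenting roll-overs: 44.8% by simulation. This is an upper bound, because a patient with an unseen early recurrence is assumed never to have one counted later.

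**Recurrence, consented retrospective patients with charts captured** (f = 50%, L = 36). If recurrence is independent of death, Kaplan-Meier recurrence stays at 60.0%. The 60-month competing-risk cumulative incidence rises from 45.5% to 48.9%, because early deaths that would have pre-empted a recurrence are missing. In a simulation with the death hazard doubled after recurrence, Kaplan-Meier falls by 0.5–0.8 points. Cumulative incidence then reads 48.3% at 60 months and dips 0.3 points at 12 months.

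**The case against.** **Roll-overs.** A reader might infer that every roll-over patient is guaranteed alive from ablation to consent. The documents do not support that. Protocol 7.1 describes the registry as an optional part of other studies, so some may have consented at or before ablation and carry no guaranteed time. Note 2, and the allowance in Protocol 7.4 for patients from previous trials, suggest that others joined later. The mix is unknown.

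**Recurrence.** A reader might also infer that recurrence is biased downward throughout. That is supported only for late-consenting roll-overs. Consented retrospective patients are selected on being alive, not on being free of recurrence, and their charts can supply earlier recurrences. For them Kaplan-Meier recurrence is close to unbiased and cumulative incidence is too high at later times. The effect on the Cox model in SAP 8.10 was not quantified, and no claim is made about it.

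**Size.** With few late entrants and short lags, the bias is well inside the confidence interval. Waiver enrolment of patients who have died would reduce it, and Protocol 9.3 asks sites to try to approach all eligible patients. It does not require complete capture of deaths, so this softens the concern without removing it.

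**Silence.** The SAP omits the risk set and does not prescribe a wrong one. But plain Kaplan-Meier with the protocol's ablation origin leads a programmer to the naive analysis.

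**Conclusion.** The point holds for overall survival in patients who consent after ablation, and for recurrence-free survival through its death component. The direction is upward unless every pre-consent death is captured by waiver. Roll-overs who consent at or before ablation are unaffected, as are fully retrospective patients entered by waiver without regard to survival.

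The size cannot be found from the documents. With true 5-year survival assumed at 50%, it runs from about 0.4 to 9.7 points over the four cases shown, against a half-width of 2.5 points. It would therefore be wrong to say that the published figures will be overstated by more than their intervals. They could be, and the plan contains nothing that would reveal it. The figures rest on exponential survival, uniform lag, and lag independent of survival.

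This is a should-fix. The endpoints are secondary and descriptive, no hypothesis is tested, and the size is unknown. The correction is mostly SAP text.

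**What to change.** In SAP 8.6:

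1. Set time zero as the ablation date for all patients. For late-consenting roll-overs and consented retrospective patients, set entry time as the later of ablation and consent.
2. Use left-truncated (counting-process) risk sets for overall survival and recurrence-free survival, and in SAP 8.5 for the competing-risk cumulative incidence of recurrence.
3. Where a site enrolled all consecutive ablations, including deaths, under a waiver, enter all its patients at Day 0. Delayed entry for only its consented patients would itself be biased there.
4. Report overall survival, recurrence-free survival and target lesion recurrence in patients who consented at or before ablation, alongside the pooled result. Where waiver capture is only partial, neither entry rule is exact, and this result is the reference.
5. For late-consenting roll-overs, link parent-study Visit 2–3 and recurrence data where consent allows. Otherwise leave them out of technical success, technique efficacy and recurrence. Without a Visit 3 result, the SAP 8.5 exclusion of technique-efficacy failures cannot be applied to them.

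Cost: early risk sets become smaller, and recurrences documented in charts before consent are not counted in the delayed-entry analyses. The list of data elements in Protocol 19.1 has no enrolment route, so it must be derived by comparing consent and ablation dates. Identifying complete-capture sites needs a site-level check, and linkage needs access to the parent databases. Survival estimates would be somewhat less favourable.

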It is the Investigator's responsibility to assess the relationship between all AEs to the registry device and procedure. All SAEs, regardless of relationship to the study device or procedure will be collected. Adverse events deemed to have an unlikely, possible, probable, or causal relationship to the procedure or device should be captured in source as part of the study and entered in the the AE eCRF. Adverse events deemed to be not related to the procedure or device should only be captured in source. The following guidelines should be used in determining the relationship of an AE to a device, procedure, or other causality:

Not related	
Relationship to the procedures or device can be excluded when:
 
 • The event is not a known side effect of the product category the device belongs to or of similar device and procedures; • The event has no temporal relationship with the use of the device or the procedures; • The event does not follow a known response pattern to the device (if the response pattern is previously known) and is biologically implausible; • The discontinuation of the device application or the reduction of the level activation/exposure (when clinically feasible) and reintroduction of its use (or increase of the level of activation/exposure), does not impact on the event; • The event involves a body-site or an organ not expected to be affected by the device or the procedure; • The event can be attributed to another cause (e.g. an underlying or concurrent illness/clinical condition, an effect of another device, drug, treatment, or other risk factors); • Harms to the subject are not clearly due to use error; or • To establish the non-relatedness, not all the criteria listed above might be met at the same time, depending on the type of device/procedure and the event.
Unlikely*	
The relationship with the use of the device seems not relevant and/or the event can be reasonably explained by another cause, but additional information may be obtained.

Possible*	The relationship with the use of the device is weak but cannot be ruled out completely. Alternative causes are also possible (e.g. an underlying or concurrent illness/condition and/or an effect of another device, drug, or treatment). Cases where relatedness cannot be assessed, or no information has been obtained should also be classified as possible.

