8.13 Safety Analyses

All AEs reported during the study will be coded to the Medical Dictionary for Regulatory Activities (MedDRA). All AEs will be summarized by MedDRA system organ class (SOC) and preferred term (PT). Separate summaries will be provided for device-related and procedure-related AEs. Serious AEs will be summarized in a similar manner. All reported adverse events will be listed.

Ninety-five percent confidence intervals may be provided for pre-specified adverse events of interest, which are:

- Ascites (accumulation of fluid causing abdominal swelling)
- Biloma/bile leak (buildup of bile within the abdomen)/bile leak)
- Bile duct injury
- Bleeding requiring transfusion, embolization (obstructing of blood vessel or organ to stop bleeding), or prolonged hospital stay
- Intrahepatic hematoma
- Pneumothorax and hemothorax
- Organ injury other than the liver (such as gastrointestinal injury/perforation, diaphragmatic injuries/hernia)
- Fever
- General feeling of tiredness
- Infection
- Liver dysfunction
- Liver abscess
- Nausea
- Pain
- Pneumonia
- Pleural effusion

- Post ablation syndrome, which is your body's response to the destroyed lesion. You may experience flu-like symptoms, including fever, decreased appetite, and general discomfort. This syndrome generally happens 3 to 5 days after the ablation procedure.
- Skin burn
- Thrombosis (local coagulation or clotting of the blood in the circulatory system, with/without tube drainage)
- Tumor implantation

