8.14 Additional Endpoint Analyses

Not applicable.

9 Data Monitoring Committee (DMC)

Not applicable.

10 Appendix: Tables, Listings and Graphs Shells

Table shells are provided in a separate document for all summaries to be generated for this study. These shells are a guide to the general layout of data to be presented. Minor modifications can be made to suit existing programs or macros that are available. Additionally, a list of all listings to be created is provided corresponding to the eCRFs that are used in this study. All fields collected will be listed.

Signature Page for VTMF-24375215, V-TMF Version: 1.0
NEU_2017_04---Statistical Analysis Plan-30 Oct 2025

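### The SAP text describes no peri-procedural AE summary, and roll-over patients ablated before registry consent dilute the early-complication percentages

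*SAP*

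**What the plan says.** SAP 8.6 summarises qualifying AEs and all SAEs "from the start of the ablation procedure through the end of the study will be summarized by MedDRA system organ class" and preferred term. The period is that of the endpoint in SAP 8.4.2 item 6 and Protocol 6.3 item 6. SAP 8.13 repeats the summary for all AEs and for SAEs, and adds: "Separate summaries will be provided for device-related and procedure-related AEs". It then says: "Ninety-five percent confidence intervals may be provided for pre-specified adverse events of interest, which are", followed by the list. No interval method or denominator is stated there. SAP 8.1 provides counts and percentages for categorical data, and no other AE estimator appears.

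The safety denominator is defined in SAP 6: eligible subjects "to whom the NeuWave Ablation device was utilized during procedure. Safety endpoints will be analyzed using SAF".

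On roll-over patients, Note 2 to the protocol's Schedule of Assessments says that they "will only have data collected in the Registry database starting from the time they consent to participate in the registry", and adds: "Any data previously collected on roll-over patients will remain in the original database in which it was entered into".

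On relatedness, Protocol 13.1 says: "Adverse events deemed to have an unlikely, possible, probable, or causal relationship to the procedure or device should be captured in source" and entered in the AE eCRF. The table there marks all four grades as related. It also assigns events that cannot be assessed to the possible grade, and does not require every criterion to be met.

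SAP 10 says: "Table shells are provided in a separate document for all summaries to be generated for this study".

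**The concern.** Many of the listed AEs of interest are complications of the procedure: bleeding, pneumothorax, bile duct injury, skin burn, liver abscess, and a post-ablation syndrome that the SAP itself places at 3 to 5 days. A reader will want the risk of these around an ablation. The summaries described run for up to 5 years and, as far as the text goes, put an event after a year-3 re-ablation in the same patient-level count as one after the index ablation. The risk around the index ablation would have to be rebuilt from the listings.

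The denominator raises a separate question. A roll-over patient ablated before registry consent meets the Safety Analysis Set definition, yet the registry holds no AE data for that patient's early period. Such a patient adds to the denominator and cannot add an early event to the numerator. SAP 8.11 (no imputation) and SAP 8.7 (no sensitivity analysis) offer no remedy.

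Finally, a crude percentage over 5 years takes no account of unequal follow-up, whereas SAP 8.5 estimates target lesion recurrence with death as a competing risk.

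**Working it through.** The plan gives no AE rate, loss rate, re-ablation rate or roll-over share, so there is no figure to reproduce. Every input below is assumed except N = 1500, the planned maximum in the Protocol Summary, and the 5-year horizon.

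**1. Whole-study tables against an index window.** Take a risk of p = 0.02 per session, s sessions per patient, and T = 3 years of mean follow-up. Let same-term background SAEs occur at b = 0.005 per person-year, with a share q of them entering the table. The per-patient percentage is 1 − (1 − p)^s × exp(−b·q·T).

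| Table | s = 1.0 | s = 1.3 |
|---|---|---|
| Related events, q = 0 | 2.00% | 2.59% |
| Related events, q = 0.1 | 2.15% | 2.74% |
| All-cause SAEs, q = 1 | 3.46% | 4.04% |

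A 3-month index window (T = 0.25, s = 1) gives 2.01% at q = 0.1 and 2.12% at q = 1. With one session, then, the related-event table is 1.00 to 1.07 times the index risk. Most of the remaining excess, up to 1.37 times, comes from counting repeat sessions. The all-cause SAE table is 1.7 to 2.0 times the index risk.

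**2. Roll-over patients in the denominator.** Let f be the share of the Safety Analysis Set ablated before registry data capture. The displayed index risk is p × (1 − f).

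- f = 0.02: 0.02 × 0.98 = 1.96%
- f = 0.10: 0.02 × 0.90 = 1.80%
- f = 0.30: 0.02 × 0.70 = 1.40%

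At f = 0.10, 1350 patients are observed and 27 have an event. On the full set, 27/1500 = 1.80% (Clopper-Pearson 95% CI 1.19% to 2.61%). On the observed patients, 27/1350 = 2.00% (1.32% to 2.90%). The intervals overlap heavily.

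**3. Both effects together.** If roll-over patients contribute only their repeat sessions, the displayed figure is (1 − f)(1 − 0.98^1.3) + f(1 − 0.98^0.3). This is 2.39% at f = 0.10 and 2.00% at f = 0.30. Repeat sessions raise the figure and roll-over patients lower it; in the second case they cancel. The net direction relative to the index risk is therefore not fixed.

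**4. Loss to follow-up.** With constant hazards h (event), d (death) and l (loss) over a horizon of H years, the crude proportion is h/(h + d + l) × [1 − exp(−H(h + d + l))]. The true incidence is the same expression with l = 0. Take d = 0.08 to 0.15 per year.

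| Event timing | Annual loss hazard | Crude ÷ true |
|---|---|---|
| First month (h = 0.02/H) | 0.02 to 0.20 | 0.992 to 0.999 |
| First 3 months (h = 0.02/H) | 0.02 to 0.20 | 0.976 to 0.998 |
| Constant over 5 years (h = 0.004) | 0.02 to 0.05 | 0.89 to 0.96 |
| Constant over 5 years (h = 0.004) | 0.10 to 0.20 | 0.65 to 0.81 |

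Early events are hardly touched. Late events are understated noticeably only if loss is substantial.

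**The case against.** The SAP analyses the endpoint as defined, and incidence over the whole treatment course is a legitimate estimand: a patient with more sessions really does carry more risk. Non-serious events rated not related never reach the eCRF, and the device- and procedure-related tables are the natural complication summaries. The relatedness criteria use timing, so much late background is screened out; with one session the illustration puts those tables within 7% of the index risk. All of this stands, and it is why the whole-study tables should stay. It does not supply a figure for the index ablation, because a causality filter cannot separate sessions and admits events rated unlikely.

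A reader might infer that the SAP sets no time window at all, or that it decides to pool index and repeat ablations. Neither is supported. The window is the whole study, and pooling is inferred only from the absence of a split. The shells may contain one.

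On roll-over patients, no sentence says that they are to be counted as event-free; that follows from applying the Safety Analysis Set definition together with Note 2. SAP 1.2 also says that data from patients in other NeuWave studies will be included, and those who consented to the registry before ablation are unaffected. Other retrospective patients are also unaffected, because Protocol 13.2 has their records reviewed for reportable events. The affected group may be small, but the definition as written does not exclude it.

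On loss, AEs may be assessed by phone (Protocol 12.3), and at withdrawal sites are to make every effort to collect AEs (Protocol 7.7). Both soften the understatement of late events.

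**Conclusion.** The point holds as a minor one. The SAP text gives whole-study AE summaries only, and the Safety Analysis Set definition builds a downward bias into early-complication percentages equal to the share of roll-over patients ablated before consent. That share is unknown. At an assumed 10% the effect is a fall from 2.0% to 1.8%, within sampling error; it would take 30% to bring the figure down to 1.4%. Understatement of late-onset events depends on loss rates that the documents do not give.

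A reader might conclude that the reported complication rates will be materially wrong, or wrong in a known direction. The documents do not support that: every size above rests on assumed inputs, and the effects of repeat sessions and roll-over patients oppose each other. No test or sample size is affected. What is lost is ease of interpretation, and the data to restore it are already collected.

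**What to change.** Amend SAP 8.13 as follows.

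1. Keep the whole-study tables.
2. Add one table of related AEs, SAEs and AEs of interest with onset from the start of the index ablation to the end of the Visit 3 window (under 3 months). Show events after a repeat NeuWave ablation separately. Limit the denominator to Safety Analysis Set patients whose AEs the registry captured from the index ablation, whether prospectively or by chart review.
3. For AEs of interest named in advance as late, such as tumor implantation, give cumulative incidence with death as a competing risk in the same patients.

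The cost is SAP wording and a few tables. AE onset dates (Protocol 13.2) and re-ablation details (Protocol 12.3) are already recorded. Two choices have to be made: a rule assigning each event to a session, for instance the most recent one, and the window itself, for which 30 days is an alternative. If the shells already contain such a table, a sentence in SAP 8.13 stating its window and denominator would be enough for item 2.
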